1.2.3.1. Study GS-US-350-1599

Study GS-US-350-1599 is an open label, Phase 1 study that includes subjects with advanced solid tumors, ER+/Her2- breast cancer, and lymphomas. This study is an ongoing, multicenter,

sequential dose-escalation study to evaluate the safety, tolerability, pharmacokinetics and pharmacodynamics of GS-5829 in subjects with advanced solid tumors and lymphomas. This study includes a cohort of subjects with advanced stage breast cancer who receive GS-5829 combined with exemestane or fulvestrant. Doses planned for this study are 0.6, 1.4, 2, 3, 4, 6, 9, and 12 mg once daily.

Based on the data collected so far for GS-350-1599, the most frequently reported AEs, occurring in \geq 20% of the subjects in either group include abdominal pain, nausea, decreased appetite, fatigue, dehydration, diarrhea, hypotension, and vomiting. The majority of AEs have been \leq Grade 2. Two out of 24 subjects (8.3%) have discontinued GS-5829 due to AEs.

Two DLTs were reported as of 11 November 2016: a DLT of Grade 3 thrombocytopenia was reported in 1 subject at 3 mg, and a second DLT of adrenal hemorrhage was reported in 1 subject at 4 mg. Following the data-cut-off of 11 November 2016, two dose-limiting toxicities (grade 3 thrombocytopenia, grade 3 AST elevation) occurred in two out of 3 subjects who were dosed at the 6 mg dose level. Therefore, the single agent MTD of GS-5829 from the dose escalation portion of Group 1 of this study was determined to be 4 mg daily.

Additional information for Group 2 subjects with ER+/HER2- breast cancer are as follows: Treatment-emergent AEs were reported for 6 of the 7 subjects in Group 2: 3 in the 2-mg + exemestane group and 3 in the 2-mg + fulvestrant group. Adverse events reported by 2 or more subjects total in Group 2 included nausea (3 subjects), and vomiting, diarrhea, dehydration, and hypotension (2 subjects each). One event of vomiting was considered by the investigator to be Grade 3, and the remainder of the AEs were \leq Grade 2. All remaining AEs occurred in \leq 1 subject per treatment group. No TEAE reported in Group 2 has led to study drug discontinuation. Enrollment to this cohort has been stopped when GS-US-350-1937 was being initiated.

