Dose Level	GS-5829 (once daily)	Group A (GS-5829 + Exemestane)	Group B (GS-5829 + Fulvestrant)
1	3 mg		
2	4 mg*	25 mg orally once daily (or in accordance with locally approved labelling)**	500 mg intramuscularly on day 1, 15***, 29 and then every 28 days (or in accordance with locally approved labeling)
3	6 mg		
4	9 mg		

* The starting dose for the phase 1b was determined to be 4 mg based on safety information, PK and biomarker data from two ongoing GS-5829 studies (GS-US-350-1599, GS-US-350-1604) and the recommendation by the Bayesian Logistic Regression Model (BLRM) of dose-DLT relationship.

** Enrollment in Group A has been stopped after completion of the 4 mg GS-5829 dose level safety assessments.

*** A one-time additional dose of 500 mg fulvestrant should be administered on Cycle 1 Day 15 (C1D15) for subjects initiating fulvestrant on this study at C1D1

Group A and Group B will dose escalate independently of each other. Each dose escalation cohort will consist of 3 newly enrolled subjects who will be treated at the specified dose level. Enrollment in Group A has been stopped after completion of the 4 mg GS-5829 dose level safety assessments. Dose escalation in Group B will continue until identification of the MTD of GS-5829, or until a RP2D is reached (see rationale above).

After all the subjects in each cohort have been followed for at least 28 days after C1D1 of GS-5829 and are evaluable, a dose-DLT model (Bayesian logistic regression model, see [Appendix 10](#)) utilizing all available GS-5829 safety data will be built and will provide estimates of DLT rates at all dose levels. The recommended dose from the dose-DLT model for the next cohort will be the one having the highest probability that the DLT rate falls in the target interval (16.7%, 33.3%), and a probability of < 25% that the DLT rate exceeds 33.3%.

The dose escalation decision and the final decision for the RP2D will be made by the SRT, following a review of the model recommendation and all relevant data including safety information, pharmacokinetics, biomarkers and clinical data from evaluable subjects.

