The SRT will consist of at least one investigator and the following Gilead Sciences, Inc. (Gilead) study team members: the Gilead medical monitor, representatives from Drug Safety and Public Health (DSPH) and Biostatistics. Others may be invited to participate as members of the SRT if additional expertise is desired. The Gilead medical monitor serves as the chair of the SRT. Investigators whom have enrolled a subject into the cohort the SRT is evaluating is/are required to participate in the dose escalation/expansion decision.

The recommended dose of GS-5829 to be combined with fulvestrant in the Randomized Phase 2 Dose Expansion part of this study will be determined based on the data available in the Phase 1b Dose Escalation portion of this study and from studies GS-US-350-1599 and GS-US-350-1604. The recommended dose will not exceed the MTD identified by the Phase 1b dose escalation

from this study. At least 6 subjects should have already been treated and evaluated at that dose level prior to enrolling subjects in the Randomized Phase 2 Dose Expansion.

Dose Limiting Toxicity (DLT) Definition

A DLT is a toxicity defined below and considered possibly related to GS-5829 if occurring during the DLT assessment window (Day 1 through Day 28) in each combination therapy cohort:

[figure not shown]
- Grade ≥ 4 neutropenia (absolute neutrophil count [ANC] $< 500/\text{mm}^3$)
- Grade ≥ 3 neutropenia (ANC $< 1000/\text{mm}^3$) with fever (a single temperature of $> 38.3^\circ\text{C}$ or a sustained temperature of $\geq 38^\circ\text{C}$ for more than one hour)
- Grade ≥ 3 thrombocytopenia
- Grade ≥ 2 bleeding (e.g. gastrointestinal, respiratory, epistaxis, purpura)
- Grade ≥ 3 or higher non-hematologic toxicity, except:
 - Grade 3 nausea or emesis with maximum duration of 48 hours on adequate medical therapy
 - Grade 3 diarrhea which persists for < 72 hours in the absence of adequate medical therapy
- Grade ≥ 2 non-hematologic treatment-emergent adverse event (TEAE) that in the opinion of the investigator is of potential clinical significance such that further dose escalation would expose subjects to unacceptable risk
- Treatment interruption of ≥ 7 days due to unresolved toxicity

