Appendix 10. Bayesian Logistic Regression Model

Determination of the MTD will be based on the posterior probability of DLT rate estimated by a 2-parameter BLRM with overdose control {[Neuenschwander 2008](#)} and calculated using East software {[Cytel Inc 2016](#)}.

Let $\pi[d_i]$ be the probability of DLT at dose level d_i of GS-5829. The statistical model describing dose-toxicity relationship will have the following form:

$$\pi[d_i] = \frac{\exp(\log(\alpha) + \beta \log(\frac{d_i}{d^*}))}{1 + \exp(\log(\alpha) + \beta \log(\frac{d_i}{d^*}))}$$

where $\alpha, \beta > 0$ and d^* is the reference dose level. The prior specification of the model parameters is provided below. The estimate of parameters will be updated as data are accumulated and the toxicity probability at each dose level will be calculated based on the posterior distributions of the model parameters. The estimated posterior probability of DLT rate at each dose level will be summarized using the following intervals:

Under dosing: [0.00, 0.167)

Targeted toxicity: [0.167, 0.333]

Excessive toxicity: (0.333, 1.00]

The overdose control criterion is set as the posterior probability of excessive toxicity less than 25%. The dose level recommended for the next cohort will be the dose cohort at which the posterior probability for the target toxicity interval is maximum among all dose candidates satisfying the overdose control criterion.

The trial can be stopped if any one of three criteria is met:

1. The posterior probability of targeted toxicity exceeds 70% and at least 6 subjects have been allocated at a dose level
2. Maximum number of subjects (N=12) has been treated at a dose level
3. Maximum number of subjects (N=30) has been reached

1. Planned Dose Levels

The provisional dose levels for GS-5829 are 3 mg, 4 mg, 6 mg and 9 mg once daily.

2. Prior Specification

The prior distribution for $(\log(\alpha), \log(\beta))$ is assumed to be a bivariate normal distribution. The following non-informative prior is used first:

- The median DLT rate at 3 mg is assumed to be 15%, i.e. $\text{mean}(\log(\alpha)) = -1.73$.
- A doubling in dose is assumed to double the odds of DLT, i.e. $\text{mean}(\log(\beta)) = 0$
- The StD of $\log(\alpha)$ is set to 2 and the StD of $\log(\beta)$ to 1.
- The correlation between $\log(\alpha)$ and $\log(\beta)$ is set to be 0.

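### The Grade 3 diarrhea exception to the DLT definition turns on therapy being absent, the reverse of the nausea/emesis exception next to it, so DLT status can depend on whether care was given

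*Protocol*

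**What the plan says.** Protocol section 3.2 opens its list of non-hematologic DLTs with "Grade ≥ 3 or higher non-hematologic toxicity, except" and then gives two exceptions, one after the other:

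- The first exempts "Grade 3 nausea or emesis with maximum duration of 48 hours on adequate medical therapy", so it applies when therapy was given.
- The second exempts "Grade 3 diarrhea which persists for < 72 hours in the absence of adequate medical therapy", so it applies when therapy was not given.

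The synopsis carries both exceptions in the same words. A toxicity on the list counts if it is "considered possibly related to GS-5829 if occurring during the DLT assessment window (Day 1 through Day 28"). Two later bullets can still make an excepted event a DLT. One covers a Grade 2 or higher non-hematologic event that the investigator judges "is of potential clinical significance such that further dose escalation would expose subjects to unacceptable risk". The other covers a treatment interruption of 7 days or more for unresolved toxicity.

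The SAP states no DLT criteria of its own. Its section 3.1.4 defines the DLT Analysis Set and section 7.1.7.1 plans a by-subject DLT listing, so both rely on the protocol's definition.

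**The concern.** The two exceptions sit side by side and apply the same condition in opposite directions: adequate therapy must be present for nausea/emesis and absent for diarrhea. For diarrhea, two episodes of the same grade, duration and relatedness can be classified differently only because one site treated and the other did not.

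DLTs through Day 28 are the Phase 1b primary endpoint (protocol 8.1.2) and the toxicity data that update the dose model (3.2, Appendix 10). A subject with a DLT before Day 28 enters the DLT-evaluable set without completing the window (8.2.1.4, SAP 3.1.4), so the classification also affects who is analysed and who is replaced (6.12). Section 5.3.1 refers back to the same definition. With small cohorts ("Each dose escalation cohort will consist of 3 newly enrolled subjects"), a single classification carries weight.

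**Working it through.** **Step 1. Apply the text literally.** For possibly related Grade 3 diarrhea in Days 1-28, the event is a DLT under this bullet unless it lasted under 72 hours and adequate therapy was absent.

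| Grade 3 episode | Exception met? | Result under this bullet |
|---|---|---|
| Diarrhea, 24 h, adequately treated | No | DLT |
| Diarrhea, any duration, adequately treated | No | DLT |
| Diarrhea, 60 h, untreated | Yes | Not a DLT |
| Diarrhea, 72 h or more, untreated | No | DLT |
| Diarrhea, untreated at first, then treated | Not stated | Not stated |
| Nausea/emesis, 24 h, on adequate therapy | Yes | Not a DLT |
| Nausea/emesis, 24 h, without therapy | No | DLT |

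The synopsis and section 3.2 agree with each other, and nothing elsewhere in the protocol or SAP alters the diarrhea wording.

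**Step 2. Set up the dose model to see what one classification can do.** Inputs:

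- Model (Appendix 10): logit π(d) = log α + β·log(d/d*).
- Starting prior (Appendix 10): (log α, log β) bivariate normal, means (−1.73, 0), SDs (2, 1), correlation 0.
- Reference dose d* = 3 mg. This is an assumption. It fits the stated 15% median at 3 mg, since exp(−1.73)/(1+exp(−1.73)) = 0.15.
- History as of November 2016 (section 1.3.1), DLTs/subjects: 0.6 mg 0/2; 1.4 mg 0/1; 2 mg 0/5 plus 0/6 in combination; 3 mg 1/10; 4 mg 1/9.
- Discounting: posterior variances doubled. Appendix Table 2 does this (0.56 to 1.12; 1.02 to 2.04). Applying it to the later data is an assumption.
- Dose rule: "The overdose control criterion is set as the posterior probability of excessive toxicity less than 25" per cent; among the doses that pass, take the one with the highest probability of a DLT rate in the 16.7% to 33.3% interval.

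**Step 3. Reproduce the plan's figures.** Before any study data, the refit by grid integration gives under/target/over as follows.

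| Dose | Refit | Section 1.3.1 |
|---|---|---|
| 4 mg | 69/18/13% | 70/18/12% |
| 3 mg | 87/11/2% | 89/10/1% |

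With the July 2016 data of Appendix Table 1, the 4 mg row of Appendix Table 3 is also close (0.44/0.35/0.22 against 0.43/0.35/0.23). The 3 mg row is less close (0.75/0.23/0.01 against 0.68/0.30/0.02). The refit is good enough for illustration, not an exact copy.

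**Step 4. Move one subject from non-DLT to DLT at 4 mg.**

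| Prior | DLTs at 4 mg | Overdose probability | Model recommends |
|---|---|---|---|
| November 2016 | 0/3 | 6 mg: 14.5% | 6 mg |
| November 2016 | 1/3 | 6 mg: 40.9% | 4 mg |
| plus 2/3 DLTs at 6 mg | 0/3 | 4 mg: 5.8% | 4 mg |
| plus 2/3 DLTs at 6 mg | 1/3 | 4 mg: 22.8% | 4 mg |
| plus 2/3 DLTs at 6 mg | 1/6 | 4 mg: 8.5% | 4 mg |
| plus 2/3 DLTs at 6 mg | 2/6 | 4 mg: 25.3% | 3 mg |

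The 2/3 at 6 mg is the cohort that section 1.2.3.1 reports after the November 2016 cut-off. With it included, 6 mg is barred even after 0/3 at 4 mg (overdose probability about 35%). Leaving out the six combination subjects moves the 2/6 figure from 25.3% to 26.3%. Under the prior that Appendix Table 2 gives for simulation, 0/3 v 1/3 moves the 4 mg overdose probability from about 7% to about 31%.

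**The case against.** The strongest objection is to the size. A reader might infer that with cohorts of 3 one classification decides the next dose. The documents do not support that in general. Section 3.2 calls for all available GS-5829 safety data, and once the 6 mg cohort is included, 0/3 and 1/3 at 4 mg give the same recommendation. The 1/6 v 2/6 change needs two cohorts and rests on 25.3% against a 25% limit. The model also only recommends: the Safety Review Team decides after reviewing all relevant data. These points stand.

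A reader might also infer that the clause is certain to be used because diarrhea is common. Section 1.2.3.1 does list "abdominal pain, nausea, decreased appetite, fatigue, dehydration, diarrhea, hypotension, and vomiting" as the most frequent events in Study GS-US-350-1599, but that list covers all grades and most events were Grade 2 or lower. The diarrhea search in SAP 7.1.7.2 is not restricted to Grade 3 either. None of the DLTs reported in sections 1.2.3.1 and 1.2.3.2 is diarrhea. The clause may be used; no affected event is shown. Nor do the documents suggest that any site would withhold treatment to avoid a DLT.

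A third tempting reading is that untreated diarrhea escapes the definition. That is true only below 72 hours and only under this bullet, since the investigator-judgement and 7-day interruption bullets still apply. Those bullets can add a DLT, however; they cannot remove one assigned to a treated episode. Section 3.2 also allows the investigator and medical monitor to discuss certain toxicities, giving laboratory findings without a clear clinical correlate as its example. It does not name diarrhea, so it cannot be relied on to settle these cases.

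Finally, two different toxicities may have different exceptions, and the synopsis and body agree. That is fair, and the nausea/emesis wording is not thereby shown to be the right one. But the protocol gives no reason for reversing the condition and leaves the mixed episode unclassified.

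**Conclusion.** The wording problem holds on the literal text and needs no modelling assumption: for Grade 3 diarrhea under 72 hours, DLT status under this bullet depends on whether adequate therapy was given, in the opposite direction to nausea/emesis, and a later-treated episode has no stated classification.

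The effect on the dose recommendation is possible but depends on the prior. It changes the dose at 0/3 v 1/3 with the November 2016 data, does not with the 6 mg cohort added, and is marginal at 1/6 v 2/6. These figures assume a 3 mg reference dose and doubled variances.

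SAP section 1 states that the study stopped during escalation and that all Phase 1b subjects are off drug, so no dosing decision can now change. What remains exposed is the DLT listing, the DLT Analysis Set and any MTD or RP2D statement, and only if a qualifying event occurred. The correction is worth making because the definition feeds the primary endpoint and the cost is small.

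**What to change.** Reconcile the diarrhea exception with the nausea/emesis exception in the synopsis and section 3.2. The sponsor's clinical team should state the intended condition, say so explicitly if the difference is deliberate, and say how an episode treated part-way through is classified. This review takes no position on which condition is right.

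Because escalation has ended, also check every Grade 3 diarrhea event in Days 1-28. Report in the DLT listing, and in any MTD or RP2D statement, how each was classified and under which reading. If there were none, one sentence saying so closes the point.

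The cost is one line in two places plus a short review of data already due to be listed: adverse events with grade (SAP 7.1.6.1 and 7.1.7.2) and concomitant medications (SAP 7.4.2). No extra procedures or subjects are needed.

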3.3. Study Treatments

Subjects who meet eligibility criteria will receive GS-5829 orally once daily combined with either 25 mg of exemestane orally once daily or with fulvestrant intramuscularly on Day 1, 15 (for whom C1D1 is the subject's first dose of fulvestrant), 29 and then every 28 days (\pm 3 days). Subjects in the Phase 1b Dose Escalation portion may initiate exemestane (Group A) or fulvestrant (Group B) any time prior to, or on, C1D1. Each cycle will consist of 28 days. Safety and efficacy assessments will occur on an outpatient basis including an assessment of tumor response, physical exam, vitals, ECG, collection of blood samples (for routine safety labs, GS-5829 pharmacokinetic, pharmacodynamic markers, and biomarkers at applicable visits), and assessment of AEs. In addition, subjects will undergo a CT scan (or MRI) scan every 8 weeks for the first year, then every 12 weeks.

Subjects who do not show evidence of disease progression may continue receiving GS-5829 combined with either exemestane (Group A) or fulvestrant (Group B) until disease progression (clinical or radiographic), unacceptable toxicity, withdrawal of consent, or death, whichever comes first.

Following treatment discontinuation, subjects will be followed for safety for 30 days from last dose of study drug. Subjects in the Randomized Phase 2 Dose Expansion portion of the study will also be followed for up to two years for OS from the last dose of study drug.

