A subject who does not show evidence of disease progression may continue receiving GS-5829 once daily and exemestane (Group A) or fulvestrant (Group B) until disease progression (clinical or radiographic), unacceptable toxicity, withdrawal of consent, or death whichever comes first.

Following treatment discontinuation, subjects will be followed for safety for 30 days from the last dose of study drug. Pharmacokinetic and pharmacodynamic samples for GS-5829 will be collected on Day 1 and Day 15 of Cycle 1 at pre-dose, 0.5, 1, 2, 3, 4, 6, 8 and 24 hours post-dose and anytime on Day 1 of Cycles 2 through 6.

Randomized Phase 2 Dose Expansion

Sparse pharmacokinetics and pharmacodynamic samples will be collected at pre-dose and anytime between 1 to 4 hours post-dose on Day 1 and Day 15 of Cycle 1 and at pre-dose on Day 1 of Cycles 3 and 6. Note: pharmacokinetic samples will only be collected for subjects who are randomized to a GS-5829 in combination with fulvestrant arm (Arm 1).

Subjects in the Randomized Phase 2 Dose Expansion portion of the study will also be followed for up to two years for OS.

Test Product, Dose, and Mode of Administration:

GS-5829 will be supplied as round, plain-faced tablets containing 1 mg or 5 mg GS-5829. GS-5829 tablets will be self-administered orally once daily, beginning on C1D1 of the study and thereafter at approximately the same time each day until end of treatment (EOT).

For subjects in Group A of the Phase 1b Dose Escalation, 25 mg exemestane tablets will be self-administered orally once daily (or in accordance with locally approved labeling), beginning on C1D1 of the study and thereafter at approximately the same time each day until the EOT.

For subjects in Group B of the Phase 1b Dose Escalation or subjects in Arm 2 of the Randomized Phase 2 Dose Expansion, fulvestrant will be administered intramuscularly (in accordance with locally approved labeling) by the clinic staff approximately every 28 days (\pm 3 days) until the EOT.

For subjects in the Phase 1b Dose Escalation or subjects in the Randomized Phase 2 Dose Expansion part of the study for whom are treatment naïve (in metastatic setting) and for all subjects for whom C1D1 is the subject's first dose of fulvestrant, a one-time additional dose of 500mg fulvestrant will be administered on Cycle 1, Day 15 (\pm 3 days).

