3.6. Criteria for Removal from Study

Subjects may be removed from the study for the following reasons:

- Documented progression of malignant disease
- Death
- Investigator discretion
- Withdrawal of consent
- Lost to follow-up
- Important protocol deviation
- Pregnancy
- Study termination by the sponsor

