6.7. Long-Term Survival Follow-Up

Randomized Phase 2 Dose Expansion subjects will participate in long-term survival follow-up. These subjects will be contacted via phone call every 3 months (+/- 7 days) for determination of long-term survival status and record of any other anti-cancer therapy for up to 2 years after the last dose of study drug. For subjects who discontinued the study for reasons other than disease progression, the investigator should obtain information on the subject's post-study anti-cancer therapies, surgeries, and date of definitive disease progression (if known).

Subjects who are alive at the time the sponsor has made the determination the study will be ended will receive a final follow-up phone call to assess survival status and communicate the sponsor's decision. These subjects will be censored on the date the subject was last contacted.

The investigator will make every effort to contact the subject or a close relative or caretaker by phone to collect survival information. The investigator should show due diligence by documenting in the source documents steps taken to contact the subject i.e., dates of phone calls, registered letters, etc.

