8.1.3. Secondary Endpoints

Phase 1b Dose Escalation:

- GS-5829 pharmacokinetic parameters (e.g., C_{max} , AUC_{tau})

Randomized Phase 2 Dose Expansion:

- Overall safety profile will be characterized by the type, frequency, severity, timing of onset, duration, and relationship to study treatment of any AEs or abnormalities in laboratory tests or ECGs
- ORR, defined as the proportion of subjects who achieve CR or PR, based on RECIST v. 1.1
- CBR, defined as the proportion of subjects who achieve CR, PR or SD that lasts for ≥ 24 weeks based on RECIST v. 1.1
- OS, defined as interval from date of randomization to date of death from any cause

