- 2 Screening and EOT Physical Examinations (PE) will be a complete PE. Beginning at C1D1, a modified physical examination will be performed. Weight (without shoes) should be measured at each PE. Height (without shoes) is measured at Screening only.
- 3 ECOG will be scored using the scale index in Appendix 6
- 4 C1D1 Vital Signs will be taken within 15 minutes pre-GS-5829 dose and 2 and 4 hours post dose (+/- 15 min); vital signs will be taken pre-dose only at all subsequent visits.
- 5 Triplicate ECGs will be collected at any time during Screening window, C1D1, Day 1 of Cycles 2-6 (at pre-dose), and at EOT. In the Phase 1b Dose Escalation phase of the study, triplicate ECGs will be collected on C1D1 at pre-dose and 1-4 hrs post-dose and on C1D15 at pre-dose, 1 hour, 2 hours, 3 hours, 4 hours, 6 hours, and 8 hours post dose (\pm 20 minutes). In the Randomized Phase 2 Dose Expansion phase of the study, triplicate ECGs will be collected on C1D1 at pre-dose and 1-4 hrs post-dose and on C1D15 at pre-dose, 1 hour, 2 hours, 4 hours, and 6 hours post dose (\pm 20 minutes). ECGs should always be collected prior to pharmacokinetics (or any other blood draw) if they are to be collected at the same nominal time point. Subjects should be resting quietly and free of distraction (e.g., TV, conversation) for 10 minutes prior to ECG collection and ECGs should be collected over a 5 minute window at each time point.
- 6 Multigated acquisition scan (MUGA) is acceptable. The same modality must be used throughout study participation.
- 7 Day 1 pre-GS-5829 lab samples may be drawn up to two days prior to the Day 1 visit.
- 8 For Phase 1b Dose Escalation subjects, the 30-Day Safety Follow-Up Visit (\pm 5 days) will be the final study visit. Randomized Phase 2 Dose Expansion subjects will complete the 30-Day Safety Follow-Up Visit (\pm 5 days) and proceed to Long Term Survival Follow-Up.
- 9 LTFU will begin for subjects participating in the Randomized Phase 2 Dose Expansion phase of the study after the 30 day Safety Follow-Up visit for up to 2 years after the last dose of study drug. A phone call will be made every 3 months (\pm 7 days) to confirm whether subject has had disease progression.

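### OS is timed from randomization, but survival follow-up ends two years after each subject's own last dose, and two passages conflict with collecting deaths after progression

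*Protocol*

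**What the plan says.** - **Time origin.** Protocol Section 8.1.3: "OS, defined as interval from date of randomization to date of death from any cause". Section 8.5.2 compares the arms by log-rank test, with Kaplan-Meier estimates and hazard ratios.
- **Follow-up window.** Section 3.3 ends it two years after the last dose: subjects in the randomized Phase 2 "portion of the study will also be followed for up to two years for OS from the last dose of study drug". Sections 6.7, 6.11, 6.14 and Appendix 2 footnote 9 use the same anchor. The synopsis has subjects "followed for up to two years for OS" and names no starting point.
- **Study end.** The general OS censoring statement is in Section 6.7 and covers subjects alive when the sponsor ends the study: "These subjects will be censored on the date the subject was last contacted". No cut-off date is given.
- **Removal.** Section 3.6 lists "Documented progression of malignant disease" among the reasons for which a subject may be removed from the study. It makes no exception for Phase 2 survival follow-up.
- **Purpose of the call.** Footnote 9 says it is made "to confirm whether subject has had disease progression", and note 9 under SAP Appendix 1 repeats this. Section 6.7 says it is "for determination of long-term survival status and record of any other anti-cancer therapy for up to 2 years after the last dose of study drug". Sections 6.11 and 6.14 agree with 6.7, and Section 6.6 sends Phase 2 subjects on to long-term follow-up with no exception for progression.

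**The concern.** The end of the OS window is set by something that happens after randomization. Treatment runs to progression, unacceptable toxicity, withdrawal or death (Section 3.4), so the last dose usually tracks PFS, the endpoint on which the arms are expected to differ. A subject who progresses early leaves survival follow-up early. Beyond month 24 the risk set is increasingly made up of subjects who stayed on treatment longer. If they also live longer after that point, censoring is informative, and neither the log-rank test nor the Kaplan-Meier curve allows for it.

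The second problem is separate. A site that applied Section 3.6 literally, or asked only the question in footnote 9, could fail to record deaths after progression. OS of the combination against fulvestrant alone is a stated secondary objective.

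**Working it through.** **1. The plan's own figures.** The documents give no OS median, event count or power, so the check starts from the PFS design in Section 8.9: medians 4 and 8 months, 40 and 80 subjects, uniform accrual over 9 months, 19 months in total, 10% drop-out by 12 months. With exponential PFS, expected events are 35.0 + 53.9 = 88.9 (88 stated). Schoenfeld power at hazard ratio 4/8 = 0.5, one-sided 0.1, 2:1, is 96.3% at 88 events (above 90% stated) and 81.2% at 44 (80% stated). The PFS inputs therefore reproduce.

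**2. When the window closes.** Take last dose = progression, so the window closes at PFS + 24 months. For a PFS median m, the quartiles are 24 + m·log2(4/3), 24 + m and 24 + 2m.

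| Arm | m | Lower quartile | Median | Upper quartile |
|---|---|---|---|---|
| Fulvestrant alone | 4 | 25.7 | 28 | 32.0 |
| Combination | 8 | 27.3 | 32 | 40.0 |

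No dosed subject can be censored by the window before month 24, so it censors nobody within the planned 19 months. That duration belongs to the PFS design.

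**3. Kaplan-Meier at 36 months.** Assumptions, none from the documents: exponential OS with median 30 months, Gaussian-copula correlation with PFS of 0.3, 0.6 or 0.8, OS at least PFS, no calendar cut. Simulation with 200,000 subjects per arm:

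| Correlation | Control: estimate vs true | Excess (points) | Combination: estimate vs true | Excess (points) |
|---|---|---|---|---|
| 0.3 | 0.458 vs 0.435 | 2.3 | 0.461 vs 0.450 | 1.1 |
| 0.6 | 0.486 vs 0.437 | 4.9 | 0.465 vs 0.440 | 2.5 |
| 0.8 | 0.501 vs 0.435 | 6.6 | 0.466 vs 0.435 | 3.1 |

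Repeat runs agree within 0.3 point. Month-24 survival is unbiased.

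A second model sets OS = PFS + post-progression survival (median 12 to 30 months, equal in both arms). If the two parts are independent, the excess is at most about 0.3 point in control and about 1 point in the combination arm. At correlation 0.4 it is about 2 to 4 and 2 to 3 points.

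**4. Hazard ratio for OS.** Copula model, full follow-up versus the window. Month 33 is an illustrative calendar cut (9 months' accrual + 24).

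| Correlation | No calendar cut | Month-33 cut |
|---|---|---|
| 0.3 | 0.968 to 0.941 | 0.915 to 0.915 |
| 0.6 | 0.985 to 1.004 | 0.964 to 0.973 |
| 0.8 | 1.000 to 1.054 | 0.995 to 1.010 |

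In the second model the month-33 shift is 0.01 or less. For a post-progression median of 24 months it is 0.739 to 0.731 (independent) and 0.799 to 0.802 (correlated).

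**5. Share censored by the window.** In the second model without a calendar cut, the share is the same in both arms (25% to 57%, depending on the post-progression median), only earlier in control. With the month-33 cut it is 12 to 28% of control against 8 to 18% of the combination arm (independent), or 8 to 23% against 4 to 13% (correlated).

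**6. Removal at progression.** At calendar month 19, follow-up ranges from 10 to 19 months. Without drop-out, the share progressed is 1 − [m/(9 ln 2)]·(2^(−10/m) − 2^(−19/m)), which is 91% for m = 4 and 71% for m = 8. If half of these subjects were removed at progression (illustrative), the month-19 OS hazard ratio in the second model would move from 0.63–0.66 to 0.54–0.56 (independent) or from 0.71–0.77 to 0.61–0.65 (correlated), in favour of the combination.

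**The case against.** Four sections already require survival follow-up in Phase 2, and the Appendix 2 column that carries footnote 9 is headed as survival follow-up. Section 3.6 is a general list for both phases and says only that subjects may be removed. This stands: the documents do not show that progression would end follow-up or that sites would ask only about progression. What remains is a contradiction to reconcile.

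A reader might infer that the last-dose anchor censors more control subjects and biases OS against the combination. The documents do not support either inference:

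- Earlier closure in control follows from the hoped-for 4 and 8 months. A larger censored share in control needs a calendar cut or further assumptions.
- Sections 5.3.1 and 6.5 stop both drugs together in the combination arm, which could shorten its window. Full equalization would need an added stopping hazard of ln 2/8 = 0.087 per month, or 1 − exp(−12 × 0.087) = about 65% by 12 months. The gap would therefore probably narrow rather than vanish.
- The hazard-ratio shift changes sign with the assumed correlation, and removal at progression moves it the other way.
- The copula model is not a clean null. Forcing OS to be at least PFS gives the combination arm higher true survival (0.450 against 0.435 at correlation 0.3).

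OS is also secondary with no stated power. SAP Section 1 says that the study stopped before Phase 2, and SAP Section 6 defines no OS analysis. No reported OS comparison is affected.

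**Conclusion.** The point holds as a design weakness with an inexpensive repair. The OS window depends on treatment duration, and after month 24 censoring is linked to progression and can be informative. The closing medians of about 28 and 32 months rest on the plan's PFS assumptions and on last dose coinciding with progression. The 36-month overstatement of about 2 to 7 points in control and 1 to 3 in the combination arm rests on the assumed 30-month OS median and correlations of 0.3 to 0.8; it is smaller if post-progression survival is independent of PFS. No direction of bias in the treatment comparison is established, and the hazard-ratio shift at a month-33 cut is about 0.015 or less. The conflict of Section 3.6 and footnote 9 with Sections 6.6, 6.7, 6.11 and 6.14 is textual and needs no assumption. If 3.6 were applied, deaths after progression would be lost.

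**What to change.** 1. Follow every randomized Phase 2 subject for survival from randomization to one common calendar cut-off, regardless of treatment stop or progression. Include subjects who were never dosed: they are in the ITT set (Section 8.2.1.1) but have no last dose from which to count. State the cut-off and an OS censoring rule, and align the synopsis.
2. Reconcile Section 3.6 with 6.6, 6.7, 6.11 and 6.14 so that documented progression does not end Phase 2 survival follow-up.
3. Make footnote 9 and its SAP copy match Section 6.7: survival status, date of death and subsequent anti-cancer therapy.

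The cost is protocol wording and a few extra quarterly calls for subjects who stop early. Truncating the OS analysis at 24 months from randomization is a fallback only. It adds no calls for dosed subjects, but it gives up later deaths, and the present schedule still defines no window for those never dosed.
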